### 5.10. Analysis of Pharmacokinetic Variables

**Analysis of Immunogenicity Data** 

Descriptive statistics for concentrations of total drug will be presented. Mean concentrations will be tabulated by visit and treatment group, with concentrations below the LLOQ set to zero. Plots of the mean concentrations (linear and log scales) will be presented by nominal sampling time. Plots of the individual concentrations (linear and log scales) will be presented by actual sampling time. In the linear-scaled plots, concentrations below the LLOQ will be set to zero; in the log-scaled plots, concentrations below the LLOQ will be imputed as LLOQ/2. Where appropriate, relationship between concentrations of total drug and other pharmacodynamic biomarkers including, but not limited to, changes in endpoints of interest (eg, HbA1c, glucose, and TG) may be evaluated descriptively.

Regeneron Pharmaceuticals, Inc.

Page 47 of 88

Protocol: R4461-PLD-20100

- Transient Not persistent or indeterminate, regardless of any missing samples
- Indeterminate A positive result in the ADA assay at the last collection time point only, regardless of any missing samples

Date: May 16, 2024

- The maximum titer category of each patient is classified as:
- Low (titer <1,000)
- Moderate  $(1,000 \le \text{titer} \le 10,000)$
- High (titer > 10,000)
  - Samples that are positive in ADA assay may be assessed for the presence of neutralizing anti-drug antibodies (NAb) when NAb assay is available.
- The following will be summarized by treatment group and ADA titer level:
- Number (n) and percent (%) of ADA-negative patients
- Number (n) and percent (%) of patients with pre-existing ADA
- Number (n) and percent (%) of treatment-emergent ADA positive patients
  - Number (n) and percent (%) of persistent treatment-emergent ADA positive patients
  - Number (n) and percent (%) of indeterminate treatment-emergent ADA positive patients
  - Number (n) and percent (%) of transient treatment-emergent ADA positive patients
- Number (n) and percent (%) of treatment-boosted ADA positive patients
  - Listing of all ADA titer levels will be provided for patients with pre-existing, treatment-emergent, and treatment-boosted ADA response.

#### 5.11.1. Association of Immunogenicity with Exposure, Safety and Efficacy

#### **5.11.1.1.** Immunogenicity and Exposure

Potential association between immunogenicity and systemic exposure to mibavademab will be explored by treatment groups. Plots of individual mibavademab concentration time profiles may be provided to examine the potential impact of ADA by maximum titer on these profiles.

#### 5.11.1.2. Immunogenicity and Safety and Efficacy

Potential association between immunogenicity variables and safety will be explored with a primary focus on adverse events during the TEAE period.

- Injection site reaction (serious or severe and lasting 24 hours or longer)
- Infusion reactions
- Hypersensitivity (SMQ: Hypersensitivity [Narrow])

 Potential association between immunogenicity variables and efficacy endpoints may be explored (eg, scatter plot or spaghetti plot). The safety and efficacy analyses mentioned above will be conducted using the following categories:

Protocol: R4461-PLD-20100

Date: May 16, 2024

- ADA Positive
  - Treatment-emergent
  - Treatment-boosted
- Maximum post-baseline titer category

### 5.12. Analysis of Clinical Outcome Assessment

The summary of results for clinical outcomes assessments will be presented by treatment groups (Arm 1, Arm 2) and by cohorts (Cohort A, Cohort B) containing patients from the full analysis set, unless otherwise specified.

The baseline value is defined as the last available measurement prior to the time of the first double-blind study treatment administration. All measurements, scheduled or unscheduled, will be assigned to the Global Analysis Windows (Appendix 10.2) to provide an assessment for all post-baseline visit.

For the SF-36, raw value and change from baseline will be summarized using mean, median, SD, min, max, Q1, Q3 for each post baseline visit among the SF-36 analysis set.

#### 6. DATA CONVENTIONS

The following analysis conventions will be used in the statistical analysis.

### 6.1. Definition of Baseline for Efficacy/Safety Variables

Unless otherwise specified, the baseline assessment is programmatically defined as the last available measurement prior to the time of the first double-blind study treatment administration. For patients randomized and not treated, the baseline value is defined as the last available value prior to the date of randomization.

## **6.2.** Data Handling Convention for Efficacy Variables

Rules for handling missing data for primary and secondary efficacy variables are described in Section 5.7.

## **6.3.** Data Handling Convention for Missing Data

Missing data will not be imputed in listings. This section includes the methods for missing data imputation for some summary analyses, if necessary.

#### Date and Time of First/Last Study Treatment

The date and time of study drug administration are filled in e-CRF. No missing data is expected. Date of first/last administration is the first/last start date of study drug provided in e-CRF.

Regeneron Pharmaceuticals, Inc.

Page 49 of 88

#### **Adverse Event**

If the intensity of a TEAE is missing, it will be classified as "severe" in the frequency tables by intensity of TEAEs. If the assessment of relationship of a TEAE to the investigational product is missing, it will be classified as related to the investigational product.

When the partial AE date/time information does not indicate that the AE started prior to study treatment or after the TEAE period, the AE will be classified as treatment-emergent.

#### Medication/Procedure

No imputation of medication/procedure start/end dates or times will be performed. If a medication date or time is missing or partially missing and it cannot be determined whether it was taken prior or concomitantly or stopped prior to the first study treatment administration, it will be considered as concomitant medication/procedure.

### Potentially Clinically Significant Value (PCSV)

If a patient has a missing baseline value, this patient will be grouped in the category "normal/missing at baseline."

For PCSVs with 2 conditions, one based on a change from baseline value and the other on a threshold value or a normal range, with the first condition being missing, the PCSV will be based only on the second condition.

For a PCSV defined on a threshold and/or a normal range, this PCSV will be derived using this threshold if the normal range is missing. For example, for eosinophils, the PCSV is >0.5 giga/L or >ULN if ULN  $\geq$ 0.5 giga/L. When ULN is missing, the value 0.5 should be used.

Measurements flagged as invalid by the laboratory will not be summarized nor included in the computation of PCSVs.

#### 6.4. Visit Windows

Visit windows will be programmatically imposed on those efficacy and safety measures repeatedly collected over the course of the study. These visit windows are derived from the number of days in study, specifically assigning day ranges to represent the study assessment schedule provided in the protocol. Data analyzed by time point (including efficacy, laboratory safety data, vital signs, and ECG) will be summarized using the analysis windows given in Appendix 10.2. These analysis windows will be applicable for all efficacy and safety analyses, and they are defined to provide more homogeneous data for time point-specific analyses. If multiple valid values of a variable exist within an analysis window, the nearest from the targeted study day will be selected for analysis, unless otherwise specified. If the difference is a tie, the value after the targeted study day will be used. If multiple valid values of a variable exist within a same day, then the first value of the day will be selected when time is available, else the scheduled visit will be selected.

#### 6.5. Unscheduled Assessments

For efficacy, safety laboratory data, vital signs, and ECG, unscheduled visit measurements may be used to provide a measurement for a time point, including baseline, if appropriate according

Regeneron Pharmaceuticals, Inc.

Page 50 of 88

Protocol: R4461-PLD-20100

to their definitions. The measurements may also be used to determine abnormal values, AESIs, and PCSVs.

#### **6.6.** Pooling of Centers for Statistical Analyses

Not applicable.

#### 6.7. Statistical Technical Issues

Not applicable.

#### 7. TIMING OF STATISTICAL ANALYSES

#### 7.1. Interim Analysis

No formal interim analysis is planned. Periodic data reviews may be performed by selected unblinded Regeneron personnel with no direct involvement in the study conduct.

### 7.2. First Step Analysis

The first-step analysis will be conducted as soon as all patients have been randomized and all data through week 12 has been entered, cleaned, and locked. The first-step analysis will be conducted on all randomized patients who receive study treatment. These statistical analyses will include the primary and secondary endpoints collected during the double-blind period. All subsequent protocol work can be generated in an unblind-blind manner (study treatment assignments, primary efficacy variables, and applicable secondary efficacy variables), excluding the investigative sites.

### 7.3. Second Step Analysis

The second step analysis will be conducted as soon as all patients have been randomized and all data through week 24 has been entered, cleaned, and locked. The second-step analysis will be conducted on all randomized patients who receive study treatment. These statistical analyses will include the secondary endpoints collected during the single-blind period.

### 7.4. Final Analysis

The final analysis will be conducted at the end of the study, and will consist of the final analysis for efficacy, pharmacokinetic and safety measures.

#### 7.5. Additional Rules

Analyses methods and conventions described in the other sections of this SAP will be applied for all analyses as applicable. The following additional rules will apply for the first-step analysis:

 Any assessments within the Efficacy Analysis Windows (Appendix 10.2) up to the SBTP week 24 visit will be taken into account (may include few unscheduled lipid data soon after the cut-off date).

Protocol: R4461-PLD-20100

• Patients without end of treatment visit performed at the time of the cut-off date will be considered as ongoing and exposed up to the cut-off date.

Protocol: R4461-PLD-20100

Date: May 16, 2024

- Patients who did not complete the respective treatment period nor prematurely discontinued the study treatment at cut-off date will be:
  - Analyzed as "ongoing" in the disposition summary.
  - Their TEAE period and treatment period will end at the respective data cut-off date.
  - Their treatment duration will be derived by considering date of cut-off as last administration date.
  - Analyses of number of IP administrations, and mean IP administration frequency will be performed up to the last administration reported in the e-CRF up to the cut-off date.
  - AEs occurring, worsening or becoming serious after the cut-off date will not be included in the analyses. However, any available outcome before database lock, regardless of timing in relation to the cut-off date, of an adverse event starting prior to the cut-off date will be taken into account. Medications, treatment discontinuations/completions and deaths occurring after the cut-off date will not be included in the analyses.
  - Post-treatment period, and post-study period are not applicable for ongoing patients. Analyses of post-study deaths and post-treatment medications will be performed for patients who either completed or prematurely discontinued the treatment before or at the data cut-off date.
  - Analysis of status at last study contact and proportion of patients with insufficient follow-up will be provided for patients who either completed or prematurely discontinued the treatment before or at the data cut-off date.

#### 8. SOFTWARE

All analyses will be done using SAS Version 9.4 or higher.

#### 10. APPENDIX

### 10.1. Summary of Statistical Analyses

#### **Primary Efficacy Analysis:**

Endpoint	Analysis Populations	Statistical Method	Supportive Analysis	Subgroup Analysis	Other Analyses
Primary Endpoint					
• Change in HbA1c from baseline to week 12 in patients with elevated baseline HbA1c (ie, screening HbA1C > 7%).	Glycemic Analysis Set – Cohort A	MMRM		No	
• Percent change in fasting triglyceride (TG) from baseline to week 12 in patients with elevated screening baseline fasting TG (ie, fasting TG ≥ 200 mg/dL).	Triglyceride Analysis Set – Cohort A	MMRM	Ranked ANCOVA	No	

### **10.2.** Windows for Analysis Time Points

Below are the definitions for the visit windows programmatically imposed on measures repeatedly collected over the course of the study. These visit windows reflect the study schedule of assessments as described in the protocol.

The visit windows are constructed using ranges applied to the number of days in study (study days) when the measure is collected. Below are the relevant definitions for the analysis visit windows:

1. Study day is defined as the number of days since the first study treatment administration +1. The first study treatment occurs on Day 1.

Protocol: R4461-PLD-20100

2. Single-blind study day is defined as the number of days since the first single-blind study treatment administration+1. Especially, Single-blind Study Day 1 (SB Day 1) is defined as the day for the first single-blind study treatment administration.

Protocol: R4461-PLD-20100

- 3. Since the protocol specifies that measurements be collected before study treatment is administered on a given day, it is appropriate that baseline include Day 1.
- 4. For randomized but not treated patients, Day 1 is the day of randomization.

**Table 8: General Global Analysis Windows** 

Visit Label	Targeted DBTP Study Day	Targeted SBTP Study Day	Analysis Window in DBTP Study Days	Analysis Window in SBTP Study Days	
Screening	< Day -28	N/A	Measurement obtained prior to 1st study trt, and not defined as baseline visit	N/A	
Baseline	Day 1	N/A	Measurement obtained closest to 1st study trt, while remaining prior to 1st study trt.admin	N/A	
Week 1	8	N/A	Day 2 to Day 15	N/A	
Week 3	22	N/A	16 to 32	N/A	
Week 6	43	N/A	33 to 50	N/A	
Week 8	57	N/A	51 to 64	N/A	
Week 10	71	N/A	65 to 78	N/A	
Week 12	85	N/A	79 to SB Day 1	N/A	
Week 13	N/A	SB Day 8	N/A	SB Day 2 to 15	
Week 15	N/A	22	N/A	16 to 29	
Week 17	N/A	36	N/A	30 to 39	
Week 18	N/A	43	N/A	40 to 50	
Week 20	N/A	57	N/A	51 to 64	
Week 22	N/A	71	N/A	65 to 78	
Week 24	N/A	85	N/A	79 to 92	
FU- W5	Last study trt admin day + 35 days	Last study trt admin day +15 days TO last study trt admin day + 49 days			
FU-W9	Last study trt admin day + 63 days	Last study trt admin day + 50 days TO last study trt admin day + 77 days			
FU-W13	Last study trt admin day + 91 days	Last study trt admin day + 78 days TO last study trt admin day + 105 days			
FU-W17	Last study trt admin day + 119 days	Last study trt adı	min day + 106 days TO la 126 days	st study trt admin day +	

**Table 9: Analysis Windows for Vital Sign** 

Visit Label	Targeted DBTP Study Day	Targeted SBTP Study Day	Analysis Window in DBTP Study Days	Analysis Window in SBTP Study Days
Screening	< Day 1	N/A	Measurement obtained prior to 1st study trt, and not defined as baseline visit	N/A
Baseline	Day 1	N/A	Measurement obtained closest to 1st study trt, while remaining prior to 1st study trt.admin	N/A
Week 1	8	N/A	Day 2 to Day 11	N/A
Week 2	15	N/A	12 to 18	N/A
Week 3	22	N/A	19 to 25	N/A
Week 4	29	N/A	26 to 32	N/A
Week 5	36	N/A	33 to 39	N/A
Week 6	43	N/A	40 to 46	N/A
Week 7	50	N/A	47 to 53	N/A
Week 8	57	N/A	54 to 60	N/A
Week 9	64	N/A	61 to 67	N/A
Week 10	71	N/A	68 to 74	N/A
Week 11	78	N/A	75 to 81	N/A
Week 12	85	N/A	82 to SB Day 1	N/A
Week 13	N/A	SB Day 8	N/A	SB Day 2 to 11
Week 14	N/A	15	N/A	12 to 18
Week 15	N/A	22	N/A	19 to 25
Week 16	N/A	29	N/A	26 to 32
Week 17	N/A	36	N/A	33 to 39
Week 18	N/A	43	N/A	40 to 46
Week 19	N/A	50	N/A	47 to 53
Week 20	N/A	57	N/A	54 to 60
Week 21	N/A	64	N/A	61 to 67
Week 22	N/A	71	N/A	68 to 74
Week 23	N/A	78	N/A	75 to 81
Week 24	N/A	85	N/A	82 to 92
FU- W5	Last study trt admin day + 35 days	Last study trt a	dmin day +15 days TO last study trt	admin day + 49 days
FU-W9	Last study trt admin day + 63 days	Last study trt ac	lmin day + 50 days TO last study trt	admin day + 77 days

Visit Label	Targeted DBTP Study Day	Targeted SBTP Study Day	Analysis Window in DBTP Study Days	Analysis Window in SBTP Study Days	
FU-W13	Last study trt admin day + 91 days	Last study trt admin day + 78 days TO last study trt admin day + 105 days			
FU-W17	Last study trt admin day + 119 days	Last study trt admin day + 106 days TO last study trt admin day + 126 days			

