8.5.1.1. Interruption of the Intravenous Infusion

The infusion should be interrupted if any of the following AEs are observed:

- Sustained/severe cough
- Rigors/chills
- Rash, pruritus (itching)
- Urticaria (hives, welts, wheals)
- Diaphoresis (sweating)
- Hypotension
- Dyspnea (shortness of breath)
- Vomiting
- Flushing

The reaction(s) should be treated symptomatically, and the infusion may be restarted at 50% of the original rate.

If investigators feel there is a medical need for treatment or discontinuation of the infusion other than described above, they should use clinical judgment to provide the appropriate response according to typical clinical practice.

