- 2. All patients will be monitored for 4 hours following infusion on day 1 and day 85. For patients undergoing apheresis, study drug will be administered after the apheresis procedure.
- 3. Monitoring by qualified study personnel may be performed as a telephone contact or an inclinic or inpatient assessment. A telephone contact may be converted to an in-person site visit if in the opinion of qualified study personnel a direct, in-person assessment would aid assessment of safety or clarify concomitant medication use and adjustment. For diabetic patients, all monitoring assessments will include asking about symptoms of hypoglycemia (per local standards), a review of the patient's home glucometer readings (if applicable), and patient education regarding the importance of blood glucose monitoring and how to recognize symptoms of hypoglycemia (per local standards). Diabetic patients should be reminded to call the site if any signs or symptoms of hypoglycemia occur.
- 4. All safety assessments should be performed before study drug administration, if possible, unless otherwise indicated.
- 5. Vital signs should be recorded prior to IV study drug infusion, and approximately 120 minutes post-IV infusion (on day 1 and day 85) and prior to SC study drug injection (on day 85).
- 6. Body weight should be measured after voiding (empty bladder) using a calibrated scale. Patients should empty pockets and remove shoes, belts, outer-layer clothing, or any other heavy wearable prior to being weighed.
- 7. Study assessments, urine, and blood (safety, efficacy and biomarkers) samples will be collected before study drug administration, unless otherwise indicated. For patients undergoing apheresis, study assessments, urine, and blood samples will be collected immediately before the lipid-apheresis procedure.
- 8. If there is a positive urine pregnancy test, a confirmatory serum pregnancy test will be performed. Study treatment will not be administered until a negative serum pregnancy test is obtained. If the serum pregnancy test is negative, the patient can continue in the study. A positive serum pregnancy test will result in permanent stopping of study drug administration.
- 9. Patients must be in a fasted state (after at least approximately a 12-hour fast). The duration of fasting may be shortened for patients with a documented clinical contraindication to fasting.

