# 4.8. Safety Variables

Patient safety will be assessed through the collection of reported adverse events (AEs), clinical laboratory data, vital signs, physical examination, and ECG. Unless otherwise noted, the baseline value is defined as the last available value before the first dose of double-blind study treatment.

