# 4.8.3. Vital Signs

Vital signs parameters will include weight (kg), height (cm), BMI (kg/m²), respiratory rate (breaths/min), temperature (C), systolic and diastolic blood pressures (mmHg), and pulse (bpm) after the patient has been sitting or in the supine position. Both actual values and "change from baseline" values (defined as the post-baseline value minus the baseline value) will be used in the result summaries, and visits will be assigned to the Global Analysis windows (see Appendix 10.2). Potentially clinically significant values (PCSV) ranges will be applied to the vital sign parameter values as applicable (see Appendix 10.4 for PCSV definitions).

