#### 5.8.5. Analysis of Vital Signs

The vital sign actual values and change from baseline values obtained will be descriptively summarized at baseline and each post-baseline visit, collected up until the day of the last dose of study treatment + 14 days.

Individual patient vital sign measurements (regardless of sitting position) will be additionally evaluated by PCSV criteria, specifically identifying patients with at least one post-baseline measurement that meets the PCSV criteria within the TEAE period. The incidence of PCSVs at any time during the respective TEAE period will be summarized regardless of the baseline level, and again according to the following baseline categories:

- Normal (according to PCSV criterion/criteria)/missing
- Abnormal according to PCSV criterion or criteria

Patient listings of vital sign measurements that meet PCSV criteria will be provided for the report appendix.

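### Vital signs taken about two hours after the Day 1 and Day 85 infusions miss the SAP's by-visit summaries: the Day 1 reading has no window, and the same-day rule drops the Day 85 reading when times are recorded

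*SAP*

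**What the plan says.** - **Schedule.** Protocol Section 9.1.2, footnote 5 to Table 2 (repeated as item 22 of SAP Section 10.7.2), asks for vital signs before the IV infusion and again "approximately 120 minutes post-IV infusion (on day 1 and day 85". On Day 85 it also asks for a reading before the SC injection.
- **Summary planned.** Protocol Section 11.4.5.2 plans change from baseline to each scheduled assessment time for temperature, pulse, blood pressure and respiration rate. SAP Section 5.8.5 has actual values and changes "descriptively summarized at baseline and each post-baseline visit", with no separate post-infusion time point.
- **Windows.** SAP Section 4.8.3 says that "visits will be assigned to the Global Analysis windows (see Appendix 10.2", and the general rules in Section 5.8 say every measurement will be given a window. For baseline, Table 9 takes the "Measurement obtained closest to 1st study trt, while remaining prior to 1st study trt.admin". SAP Section 4.8 agrees that "the baseline value is defined as the last available value before the first dose of double-blind study treatment".
- **Several values on one day.** SAP Section 6.4: "then the first value of the day will be selected when time is available, else the scheduled visit will be selected".
- **Premise.** SAP Section 10.2, item 3, justifies counting Day 1 as baseline on the ground that the protocol has measurements taken before dosing.
- **Declared departures.** SAP Section 1.2.4 lists the changes from the protocol's statistical section. None concerns post-infusion vital signs.

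**The concern.** The windows assume that every vital sign is taken before dosing. The 120-minute readings are a planned exception, and stated rules, not mere silence, keep them out of the tables.

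These readings are relevant to a harm that the protocol treats as important. Protocol Section 10.2.4 defines an infusion reaction as a relevant event during the infusion or in the 2 hours after it, so the reading falls at about the end of that interval. Moderate or severe infusion reactions are adverse events of special interest (AESIs). Hypotension is in the Protocol Section 8.5.1.1 list introduced by "The infusion should be interrupted if any of the following AEs are observed". A shift in pulse or blood pressure after the loading infusion, too small to be flagged patient by patient, would show only in a descriptive summary of change at this time point. The plan has no such summary.

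**Working it through.** No figure in the plan is at issue. The check takes each scheduled reading and assigns it under the SAP's own rules.

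**Inputs.** Table 9 (vital signs): Week 1 = Day 2 to 11, Week 12 = Day 82 to SB Day 1, Week 13 = SB Day 2 to 11, where SB Day 1 is the day of the first single-blind dose. Table 8 (global): Week 1 = Day 2 to 15, Week 12 = Day 79 to SB Day 1, Week 13 = SB Day 2 to 15. The Day 85 visit has a window of ±3 days, so SB Day 1 was placed on each of study days 82 to 88.

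| Reading | Table 9 | Table 8 | Value used by visit |
|---|---|---|---|
| Day 1, pre-infusion | Baseline | Baseline | Yes |
| Day 1, 120 min | None: after dose, before Day 2 | None: same reason | No |
| SB Day 1, pre-infusion | Week 12 | Week 12 | Yes: first value of the day |
| SB Day 1, 120 min | Week 12, not Week 13 | Week 12, not Week 13 | No, if times are recorded |

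The result is the same for all seven placements of SB Day 1 and for both tables, so it does not matter which table governs vital signs. From first dose through SB Day 15, the post-dose part of Day 1 is the only time that no window covers. When both readings are taken and timed, 0 of the 2 post-infusion time points reach the by-visit summary.

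**Two variants on Day 85.**
- *Times not recorded.* The fallback in SAP Section 6.4 is the scheduled visit. Both readings belong to the same scheduled visit, so the rule does not say which one is used.
- *Pre-infusion value missing.* The 120-minute value becomes the first of the day and enters Week 12, a double-blind time point. In Arm 1 that is a reading after active infusion reported under placebo. Table 9 does not prevent this, because its Week 12 row has no pre-dose limit on SB Day 1. Table 13 (hunger questionnaire) has that limit. For PCSVs the same reading counts as single-blind, because SAP Section 4.8.1 starts that period at the time of the first single-blind dose.

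**Number of readings.** Two per patient at most in the two treatment periods. At planned enrolment that is 40 × 2 = 80. SAP Section 1.2.4 reports early termination with limited enrolment, so the actual number is smaller and is not given.

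**The case against.** The strongest reply is that the safety information is not lost.

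- **PCSVs.** The treatment-emergent periods start at the time of first dose, and SAP Section 5.8 applies PCSV criteria to all evaluations in them. Post-infusion heart rate and systolic and diastolic pressure therefore enter the PCSV incidence tables and listings by treatment group.
- **Adverse events.** All infusion reactions must be reported. SAP Sections 5.8.2 and 5.8.3 tabulate the AESIs, the mild reactions, and infusion reactions regardless of severity. Hypotension that interrupts an infusion would appear there.
- **Few patients.** After early termination, individual flags and listings may tell more than mean changes.

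All of this stands, and it rules out several stronger readings. A reader might infer that the readings are absent from safety analysis altogether; they are not. A reader might take a fall in systolic pressure from 140 to 105 mmHg (35 mmHg) as appearing in no summary. It misses the PCSV limit in SAP Table 20 (≤90 mmHg with a fall of at least 20), but Protocol Section 10.1.1 makes it an adverse event if it is symptomatic, needs corrective treatment, or is judged one by the investigator. A reader might also call Day 1 the only randomised, blinded comparison of active with placebo infusion. Protocol Section 6.1 describes Day 85 dosing as double-blind too, with active IV in Arm 1 and placebo IV in Arm 2. Day 1 is special only because no patient has yet been exposed to the drug; on Day 85, Arm 2 has had 12 weeks of it. Nor do the documents state the purpose of the 120-minute reading; they give only its timing.

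The reply does not restore the descriptive summary. PCSV limits and adverse-event reports identify individual patients with marked changes; they do not show a group shift. Temperature and respiratory rate have no PCSV row in Table 20. That gap applies at every visit and is a separate matter, but it leaves those two signs without the PCSV route here.

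**Conclusion.** The point holds in a limited form. Under the SAP's rules the Day 1 post-infusion reading has no window. The Day 85 reading is dropped when times are recorded, is undetermined when they are not, and enters the wrong period when the pre-infusion value is missing. The by-visit summary planned in Protocol Section 11.4.5.2 is therefore not delivered for these two time points, and SAP Section 1.2.4 does not declare the omission. It looks unintended, since SAP Section 10.2, item 3, rests on a premise that item 22 of Section 10.7.2 contradicts.

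The loss is the descriptive post-infusion change, including the Day 1 comparison in unexposed patients. Endpoints, inference and adverse-event capture are unaffected. The figure of 80 readings is an upper limit at planned enrolment and should not be quoted as the actual loss. The conclusion assumes that the 120-minute reading is a scheduled assessment time in the sense of Protocol Section 11.4.5.2. Even if that phrase meant visits only, SAP Section 5.8 would still require a window for the Day 1 reading, and none exists. The early-termination bullet in SAP Section 1.2.4 cuts back efficacy analyses only, so the vital-sign summaries remain planned.

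**What to change.** 1. Add two analysis time points for vital signs to SAP Table 9, and to Table 8 where it is used for vital signs: 'Day 1 post-infusion' and 'SB Day 1 post-infusion'.
2. Exempt both from the first-value-of-the-day rule in Section 6.4.
3. Summarise the change from the same-day pre-infusion reading by IV product received. On Day 85 the double-blind group label does not name that product: the double-blind placebo group gets active IV and the other group gets placebo IV.
4. Limit the Week 12 vital-sign window to values before the first single-blind dose, as Table 13 already does, and say how the Day 85 reading before the SC injection is assigned.
5. Correct Section 10.2, item 3, so that it names the post-infusion vital signs as an exception.

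The cost is SAP wording and a few extra rows in a descriptive table. The readings are already scheduled, so no new data are needed, and clinical management does not change.
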